11.2. ADVERSE EVENTS

All systemic and skin AEs, regardless of suspected causal relationship to the investigational products, will be reported. Subject assessed skin adverse events such as skin redness (erythema), skin swelling (edema), skin bruising, skin bleeding, skin itching and skin pain are collected through the eDiary and will also be recorded as adverse events in the eCRF.

All Adverse Events (AEs) will be coded using the Medical Dictionary for Regulatory Activities (MedDRA; version 20.0 or higher). Migraine headaches will not be captured as AEs.

All AEs will be listed by subject. The following listings of AEs will be provided:

- All AEs,
- Study-drug related AEs,
- Serious adverse events (SAEs),
- AEs leading to death, and
- Adverse events leading to study-drug withdrawal.

Only TEAEs will be included in summary tables. An Overview summary table of TEAEs will be produced showing the following categories:

- Any TEAE,
- Study-drug related TEAEs,
- Serious TEAEs,
- TEAEs leading to study-drug withdrawal, and
- TEAEs leading to death.

All TEAEs will be classified by system organ class (SOC) and preferred term (PT). Frequency count and the number of unique subjects of a TEAE will be tabulated by treatment received. For the number of unique subjects reporting, if a subject reported more than one AE that was coded to the same SOC or PT, the subject will be counted only once for that specific SOC or PT.

The following summaries of TEAEs will also be provided:

- TEAEs by SOC and PT,
- Study-drug related TEAEs by SOC and PT,

- Serious TEAEs by SOC and PT,
- TEAEs by maximum severity (mild, moderate, severe or missing) by SOC and PT, and
- TEAEs by strongest causality relationship (not related, possibly related, probably related, definitely related or missing) by SOC and PT.

For TEAEs presented by relationship to study treatment(s), the strongest relationship to study treatment(s) during the study will be presented for each subject if coded to the same SOC or PT. For TEAEs presented by severity, the worst severity during the study will be presented for each subject if coded to the same SOC or PT. TEAEs with missing causality will be counted as related. TEAEs with missing severity will be counted as severe. The same will be true in the individual summaries.

TEAEs by SOC and PT and by severity and causality will be presented 3 ways: subject reported AEs from the eDiary, other subject reported AEs, and all AEs combined (eDiary and other). For subject reported AEs from the eDiary, the average time to resolution in days will be summarized.

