1 INTRODUCTION

1.1 Background

According to International Headache Society (IHS) diagnostic criteria, the prevalence of migraine has been reported to be 18% of females and 6% of males within the adult population (Lipton 2002). An estimated 37 million Americans have acute migraine attacks. Less than half receive optimal medical care.

There is still an important unmet need in treating migraine despite the availability in the last 20 years of numerous triptans that bind selectively to the 5-HT_{1B} and 5-HT_{1D} receptors. Triptans offer good efficacy and tolerability and, with several alternative formulations (intranasal and SC injection), they can overcome the gastric stasis, nausea, and vomiting that commonly accompany migraine. However, currently available triptans have several shortcomings including lack of universal efficacy, inconsistency of response, numerous adverse events, slow onset of action when administered orally, high recurrence rate and potential for Medication Overuse Headache.

Zolmitriptan is a 5HT_{1B/D} agonist widely used for the treatment of migraine. Like other compounds in the triptan class, it has been shown to be effective and well tolerated in placebo-controlled clinical trials. Zolmitriptan is available as a conventional release tablet (2.5 mg and 5.0 mg), a “fast melt” orally disintegrating tablet (2.5 mg and 5.0 mg), and a nasal spray (2.5 mg and 5.0 mg). The last two formulations were developed to potentially provide a more convenient way to take the drug versus that of the conventional release tablet.

The bioavailability of zolmitriptan conventional release tablets has been found to be between 41 and 48%, and administration with food reduced C_{max} and AUC by 13-16% (Seaber 1998). Zolmitriptan is metabolized to N-desmethyl zolmitriptan (potent active metabolite), N-oxide zolmitriptan, and indole-acetic acid metabolites. Some of the metabolites appear to be formed from first-pass metabolism. This first pass metabolism can be impacted by drugs that affect the cytochrome p-450 system. Also, absorption is reported to be lower during an actual migraine attack.

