6.1.4 Treatment Phase: Up to 12 Months

Visit 3 will be considered the “Day 1” visit for data capture purposes. Subjects will be instructed to complete the eDiary at the time of each suspected migraine attack. Once the eDiary confirms that the migraine qualifies for treatment, the subject will follow the steps provided to self-administer the study drug. If necessary, subjects may return for unscheduled visits for dispensation of additional drug kits.

The following constitutes a migraine that qualifies for treatment with study drug:

- No medication has already been taken to treat the migraine symptoms on the day of the suspected attack before applying M207.
- Presence of at least two of the following characteristics:
 - Unilateral location
 - Pulsating quality
 - Moderate or severe pain intensity
 - Aggravation by or causing avoidance of routine physical activity (e.g., walking or climbing stairs)
- During headache, at least one of the following:
 - Nausea and/or vomiting
 - BOTH photophobia AND phonophobia

The following procedures are to be started at Day 1 after receiving study medication:

- Using the eDiary, the subject will record the following to confirm the headache meets the qualifications for a migraine:
 - Migraine symptoms and pain assessment
- Once the qualifying migraine has been confirmed, subject self-administers the study drug patches. Patches cannot be applied to a previous application site unless the site is free of redness, swelling, and/or bruising. In addition, patches must not be applied to any area where the skin appears tattooed, sunburned, broken and/or irritated.
- Each set of two patches must be applied next to one another (or one above the other), on the same arm. If any skin appears broken or irritated, subsequent doses will be applied a few inches away from the previously applied patches on the same arm (or both patches on the other arm) to avoid applying in an irritated area.
- Qualifying migraine attacks cannot be treated any earlier than 48 hours after the time of patches application for a previously treated migraine attack.
- Subject will continue to record the following in the eDiary at specified time points as follows:
 - Migraine symptoms and pain assessment at the time of treatment, 30 minutes, 2 hour, 12 hours, 24 hours, and 48 hours post patch application
 - Subject reported skin assessment for bleeding at 30 minutes only

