8.2 Adverse Event Definitions

8.2.1 Adverse Events (Adverse Experiences)

Collection of systemic and cutaneous AEs will be initiated after the ICF has been signed and conclude when the post-study procedures are completed (or Early Discontinuation). This includes the time between screening and the first patch application.

An AE is any untoward medical event that occurs in a clinical investigation, where a subject is administered a medicinal (investigational) product or medical device, and which does not necessarily have a causal relationship between the event and the treatment. An AE can be any

unfavorable and unintended sign or symptom, including clinically significant abnormal laboratory result, concomitant illness, or worsening of an existing medical condition.

A Treatment Emergent Adverse Event (TEAE) is an event that emerges during treatment having been absent pre-treatment, or worsens relative to the pre-treatment state.

Abnormal laboratory tests that are clinically significant, as determined by the investigator, should be reported as AEs if:

- the test result is associated with accompanying symptoms;
- the test result requires additional diagnostic testing or medical/surgical intervention;
- the test result leads to discontinuation from the study, significant additional concomitant drug treatment, or other therapy;
- the test result is considered to be an AE by the investigator or sponsor.

Merely repeating an abnormal test, in the absence of any of the above conditions, does not constitute an AE. Any abnormal test result that is determined to be an error does not require reporting as an AE.

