8.2.1.1 Serious Adverse Event Definitions

A **serious** adverse event (SAE) or reaction is any untoward medical occurrence that at any dose:

- Results in death;
- Is life-threatening (immediate risk of death);
- Requires inpatient hospitalization or prolongation of existing hospitalization (Emergency department outpatient visits for an event not fulfilling any of the other definitions of SAE given do not qualify as hospitalization. If an emergency department visit leads to inpatient hospitalization, it would qualify as an SAE.);
- Results in persistent or significant disability/incapacity; or
- Is a congenital anomaly/birth defect.
- Other important medical events that may not result in death, be life-threatening, or require hospitalization may be considered serious when, based upon appropriate medical judgment, they may jeopardize the patient or subject and may require medical or surgical intervention to prevent one of the outcomes listed in this definition. Examples of such

medical events include allergic bronchospasm requiring intensive treatment in an emergency room or at home, blood dyscrasias or convulsions that do not result in inpatient hospitalization, or the development of drug dependency or drug abuse.

Definition of disability: A substantial disruption of a person's ability to conduct normal life functions.

Life-threatening SAE: Any AE that places the subject, in the view of the investigator, at immediate risk of death from the reaction as it occurred (i.e., it does not include a reaction that had it occurred in a more severe form, might have caused death).

Hospitalization: AEs reported from clinical studies resulting in hospitalization or prolongation of hospitalization are considered serious. Hospitalization does not include the following:

- Rehabilitation facilities;
- Hospice facilities;
- Respite care (e.g., caregiver relief);
- Skilled nursing facilities;
- Nursing homes;
- Routine emergency department admissions; or
- Same day surgeries (as outpatient/same day/ambulatory procedures).

Hospitalization or prolongation of hospitalization in the absence of a precipitating, clinical AE is not in itself an SAE. Examples include:

- Admission for treatment of a preexisting condition not associated with the development of a new AE or with a worsening of the preexisting condition (e.g., for work-up of persistent pre-treatment lab abnormality);
- Social admission (e.g., subject has no place to sleep);

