8.3 Documentation and Reporting of Adverse Events by Investigator

Each AE is to be assessed to determine if it meets the criteria for an SAE. If an SAE occurs, expedited reporting will follow local and international regulations, as appropriate.

All AEs, both expected and unexpected, occurring during this clinical trial must be recorded on the AE page of the eCRF. AEs will be described in precise medical terms, along with the date and time of onset and the date and time of resolution, action taken and outcome. In order to avoid vague, ambiguous or colloquial expressions, the AE should be recorded in standard medical terminology rather than the subject's own words. Whenever possible, the Investigator should group together into a single term signs and symptoms which constitute a single diagnosis. Each AE is to be evaluated for duration, severity, seriousness and causal relationship to the investigational drug. The severity of the AE and its relationship to the test product will be

assessed by the Investigator. When reporting SAEs, the AE form of the eCRF and the SAE form must be completed in a consistent manner. For example, the same AE term should be used on both forms.

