8.3.1 Reporting Requirements for Serious Adverse Events

ALL **SERIOUS** ADVERSE EVENTS, REGARDLESS OF CAUSE(S) OR RELATIONSHIP TO STUDY DRUG, MUST BE REPORTED **IMMEDIATELY** TO PHARMACOVIGILANCE GROUP (PV) AND MEDICAL MONITOR (MM) BY TELEPHONE (24/7 Safety Line), FAX, OR EMAIL (Contact info are provided in [Section 8.5](#)).

All SAE reporting will adhere to 21 CFR 312.32 for IND safety reporting, applicable FDA and ICH-GCP regulations.

If an SAE occurs, PV and MM are to be notified within 24 hours of awareness of the event by the investigator. In particular, if the SAE is fatal or life-threatening, notification to PV and MM must be made immediately, irrespective of the extent of available AE information. This timeframe also applies to additional new information (follow-up) on previously forwarded SAE reports. An initial assessment of causality must be included in all SAE reports.

To report an SAE, the investigator must complete the SAE Report Form, and to report a pregnancy, the investigator must complete the Pregnancy Report Form. Occurrence of any SAE/pregnancy must be reported immediately (within 1 working day) once the investigative site has knowledge of the event. The investigator must also provide any relevant information regarding the SAE and respond to requests for follow-up in a timely manner. All SAEs will also be reported on the AE CRF page and concomitant medications administered in association with the SAE will be documented on the appropriate CRF.

If an SAE occurs and comes to the attention of the investigator after study termination within 30 days of the last dose of study drug(s), it must be reported immediately to the sponsor in the same way as the SAEs occurring during the study.

8.3.1.1 Investigator Reporting Responsibilities to the Independent Ethics Committee and Other Agencies

The investigator must promptly report to the IRB/IEC or independent ethics committees (IEC) all changes in the research activity and all unanticipated problems involving risk to human subjects or others. This includes all SAEs that have occurred at the study site and all study-related SAEs that have resulted in an expedited safety report to the FDA (serious, unexpected SAEs possibly or probably related to study drug). The investigator must send all IRB/IEC documentation (including notifications and acknowledgements) to the sponsor or its

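### SAP 11.2 keeps every migraine headache out of the adverse events, with no exception for serious, worsened or withdrawal-causing migraine; this conflicts with protocol 8.2.1, 8.3 and 8.3.1 and is not declared in SAP 13

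*SAP*

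**What the plan says.** SAP 11.2 (Adverse Events) gives the rule in one sentence: "Migraine headaches will not be captured as AEs". It names no exception for seriousness, worsening, causality or withdrawal.

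The protocol says the following on the same subject:

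- Section 8.2.1: an AE includes "concomitant illness, or worsening of an existing medical condition", and an event is also treatment-emergent if it "worsens relative to the pre-treatment state".
- Section 8.3: "All AEs, both expected and unexpected, occurring during this clinical trial must be recorded on the AE page of the eCRF".
- Section 8.3.1: "All SAEs will also be reported on the AE CRF page", whatever the cause.
- Section 8.2.1.1 lists hospital stays that are not in themselves SAEs. One is "Admission for treatment of a preexisting condition not associated with the development of a new AE or with a worsening of the preexisting condition".

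None of these sections exempts migraine. SAP 13, which lists departures from the protocol's planned analysis, mentions only changes to efficacy endpoints.

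**The concern.** Leaving ordinary study attacks out of the AE data is sensible. They are the condition under treatment, and the eDiary already records them. The difficulty is that the exclusion does not stop at ordinary attacks.

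The primary objective is long-term safety of repeated use, and protocol 1.3 presents repeated treatment as what this study adds to the single-attack study. Worsening of the underlying migraine is one of the things such a study should be able to report. If the SAP sentence is applied, an empty row for it comes from the rule and not from the data. A serious migraine could also sit in the pharmacovigilance records and be absent from Table 14.3.1.4, leaving the two sources unreconciled.

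There is a classification problem as well. In the Phase 1 study (protocol Table 3) headache was reported 17 times, all under M207 regimens (3 + 2 + 4 + 4 + 4) and none under oral zolmitriptan or subcutaneous sumatriptan. In subjects with migraine, an investigator must decide whether such a headache is a migraine. The SAP gives no rule for that decision, and whatever is labelled migraine falls under the exclusion.

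**Working it through.** **1. The passages side by side**

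| Event | Under the protocol | Under SAP 11.2 as worded |
|---|---|---|
| Usual attack, treated and in the eDiary | Not a worsening; no clear duty to record as an AE | Not an AE |
| Attack clearly worse or longer than before treatment | AE and TEAE (8.2.1) | Not an AE |
| Migraine meeting an SAE criterion | SAE, and on the AE page (8.3.1) | Not an AE |
| Migraine leading to withdrawal | Site must establish whether the reason was an AE (3.2.6.1) | Not an AE |

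The documents agree on the first row. They conflict on the second and third. On the fourth, the SAP closes a question that the protocol leaves to the site. The admission exemption in protocol 8.2.1.1 applies only where the condition has not worsened, so the protocol already draws the line that the SAP sentence omits.

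**2. Which outputs are affected**

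These are the TEAE tables (14.3.1.1, 14.3.1.2a, 14.3.1.2c and those by severity), serious TEAEs (14.3.1.4), and the listings of SAEs and of AEs leading to study drug termination (16.2.7.2, 16.2.7.4).

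**3. How an empty row would read (illustration)**

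No figure in the plan can be reproduced here, since SAP 3.5 gives the sample size no statistical basis. With 0 events in n subjects, the one-sided 95% upper limit is 1 − 0.05^(1/n). The values of n are the enrolment and completion targets in protocol 3.2.1, assuming all are followed:

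- n = 250: 1.19%
- n = 150: 1.98%
- n = 50: 5.82%

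If events were captured, the chance of at least one among 250 is 1 − (1 − p)^250. For assumed true rates p of 0.5%, 1% and 2% this is 71%, 92% and 99%. Without capture it is 0 at every p.

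**4. What the other outputs would show**

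SAP 11.1 summarises treated migraines per subject per month, with Tables 14.3.2.4 and 14.3.2.5 on the Safety Population. Protocol 6.1.4 requires 48 hours between treated attacks. In the SAP's 30-day month that allows 30 × 24 / 48 = 15 treated attacks, against an entry ceiling of 8 migraines per month. A rise above the ceiling could therefore appear in Table 14.3.2.5.

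The counts are incomplete. They omit attacks for which other medication was taken first on the same day, which do not qualify (protocol 6.1.4), and attacks within 48 hours of a dose. No comparison with the pre-treatment state is planned, and the counts carry no seriousness or causality. Daily headache recording is specified for the run-in only. On treatment, "Subjects will be instructed to complete the eDiary at the time of each suspected migraine attack". That is a separate data-collection choice, but it limits how far the counts can stand in for AE records.

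**The case against.** The strongest reply is that the SAP does not instruct investigators. The protocol governs recording, the SAP lists all AEs and tabulates serious TEAEs, and it has no programmed step that removes recorded events by preferred term. A migraine SAE on the AE page would then reach Table 14.3.1.4. On this view the sentence only says that attacks already held as efficacy data are not counted twice.

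Part of this stands. The protocol's duty to report SAEs to pharmacovigilance is untouched, and events are lost only if the sentence is applied at capture or tabulation. But the sentence is a stated rule without a limit, and a programmer or data manager who follows it has no basis for keeping a serious or worsened migraine. A benign reading that the reader must supply is not a specification.

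A reader might infer three stronger things, which the documents do not support:

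- *That medication-overuse headache is barred.* The sentence covers migraine headaches only, and protocol 8.2.1.3 uses headache as an example of a recordable AE. Medication-overuse headache would be lost only if recorded as migraine. Protocol 1.1 names it ("high recurrence rate and potential for Medication Overuse Headache") as a shortcoming of available triptans, not as an M207 finding.
- *That nothing else would show worsening.* Treated-attack counts are tabulated, eDiary data are listed (16.2.6.2.1 to 16.2.6.2.4), phone contacts ask about AEs, and reasons for early termination are summarised.
- *That reported worsening is zero by construction.* This holds only if the sentence is in fact applied.

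**Conclusion.** Wrong as written. SAP 11.2 states an unqualified exclusion that has no counterpart in the protocol, conflicts with the protocol's AE and TEAE definitions and its recording rules, and is not declared in SAP 13. Applied as worded, it removes serious, worsened and withdrawal-causing migraine from the AE, serious-TEAE and withdrawal outputs. Treated-migraine counts and eDiary listings offset this in part, for frequency only.

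The conclusion rests on the text and on no assumed rate. The number of events affected cannot be estimated from the documents. The upper limits and detection probabilities above only illustrate how an empty row could be misread; they assume full follow-up and, for the probabilities, the stated rates. The correction should be made because the outputs concern the primary objective and the change is cheap.

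**What to change.** Replace the SAP 11.2 sentence with wording to this effect:

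*Migraine attacks consistent with the subject's usual pattern and recorded in the eDiary are not recorded as AEs. A migraine that meets an SAE criterion, leads to withdrawal, or is judged by the investigator to be a worsening in frequency, severity or duration from the pre-treatment state is an AE and is included in all TEAE and SAE tables. Medication-overuse headache is not covered by this exclusion.*

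Put the same wording in protocol 8.2.1, so that sites and programmers follow one rule, and record it in SAP 13.

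Optionally, tabulate all eDiary attack entries per month, qualifying and non-qualifying, as a descriptive addition to Table 14.3.2.5. Do not add a count of subjects whose entries rise from their first month. Month 1 is on treatment, so it is not a baseline, and chance alone would dominate. For two months with the same Poisson rate, the chance that the later count is higher is (1 − P(equal)) / 2. For assumed constant rates of 2 to 8 attacks per month this is 40% to 45%, and 87% to 89% of subjects would exceed month 1 at least once in the following 11 months with no true worsening.

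The cost is wording in two documents and, if the option is taken, one block from data already collected. The downside is a few more AE records and an investigator judgement on what counts as worsening.

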11.2.1. Subject Assessed Skin Adverse Events

Subject reported skin bruising, skin bleeding (at 30 minutes only), skin redness (erythema), skin swelling (edema), skin itching and skin pain at the application site are collected through the eDiary and will also be recorded as adverse events in the eCRF.

The frequencies of type of redness, severity of swelling, amount of bruising, and amount of bleeding (30 minutes only) at the application site as reported by the subject at 30 minutes, 2 hour, 12 hour, 24 hour, and 48 hours post-dose will be summarized.

The frequencies of amount of skin itching and severity of pain at the application site as reported by the subject at 48 hours post-dose will also be summarized.

Frequency tables of eDiary skin assessments will be provided using the greatest severity or greatest amount for each parameter as reported by the subject at any time during the study. The denominator will be the number of subjects in the safety population. Tables will also be generated using the data from all treated migraines so the denominator will be the number of treated migraines that have eDiary data.

The proportion of attacks and the proportion of subjects with no skin findings will be summarized by time point. Also, the proportion of attacks and subjects with any amount of all 3 symptoms (redness, swelling, and bruising) at the same time and all combinations of the 3 symptoms will be summarized by time point.

All subject assessed skin adverse events will also be listed.

The type of redness, severity of swelling, amount of bruising, amount of bleeding, amount of skin itching, and severity of pain will be collected using eDiary cards and assessed as follows:

Skin Symptom/ Time Points	Assessment
Redness (Erythema)/ at 30 minutes, 2 hour, 12 hour, 24 hour, and 48 hours post-dose	None Mild redness Moderate colored redness Beet colored redness
Swelling (Edema)/ at 30 minutes, 2 hour, 12 hour, 24 hour, and 48 hours post-dose	None Slight swelling Moderate swelling Severe swelling
Bruising/ at 30 minutes, 2 hour, 12 hour, 24 hour, and 48 hours post-dose	None Less than a quarter of the application site has bruising spots About one-half of the application site has bruising spots More than one-half of the application site has bruising spots
Bleeding/ 30 minutes post-dose only	None Pink color on skin Visible blood drop Active bleeding
Itching/ at 48 hours post-dose only	None Mild itching Moderate itching Sever itching
Pain/ at 48 hours post-dose only	None Mild pain Moderate pain Severe pain

